## 7.2.2 Assessments for Secondary Endpoints

## 7.2.2.1 Prophylactic treatment

The following parameters will be documented:

- Dates and times of study product injections
- Details of dose(s) (in IU) and product batch numbers
- Details of BEs (if any) occurring under prophylactic treatment

Study drug consumption data (FVIII IU/kg per month, per year) per patient and in total (for patients on prophylactic treatment) will be evaluated.

Efficacy Assessment of Prophylactic Treatment

The efficacy of *Human-cl rhFVIII* in prophylactic treatment will be evaluated based on the frequency of spontaneous breakthrough bleeds per months under three times weekly or every other day prophylactic treatment and will be calculated and assessed as excellent, good, moderate or poor:

Excellent:	Less than 0.75 spontaneous BEs permonth
Good:	Between 0.75 and 1 spontaneous BEs per month
Moderate:	Between more than 1 and 1.5 spontaneous BEs per month
Poor:	More than 1.5 spontaneous BEs per month

The time period for prophylactic treatment will comprise the time periods between first prophylactic treatment with *Human-cl rhFVIII* until the administration of the last prophylactic treatment + 2 days or completion visit whatever comes first) minus time periods from start of a surgery until final assessment of the surgery, and minus time period of on demand treatment, if any.

The frequency of treatment will mainly depend on the patient's clinical situation and may vary from every other day to once weekly injections. In cases of inadequate response, *Human-cl rhFVIII* administration frequency or dose adjustments can be considered at Investigator's discretion.

The number of BEs counted for prophylactic treatment efficacy assessment will comprise all BEs starting during the time periods for prophylactic treatment defined above, i.e. BEs occurring between start of surgery until final assessment of the surgery will not be included in the prophylactic treatment assessment.

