For an analysis “time / number of EDs to inhibitor occurrence” for high titre inhibitors the time defined under (I4) will be applied even if the inhibitor had started as minimum {date of $t_{1,H}$, date of $t_{1,I}$ }. For this analysis patients with confirmed low titre inhibitor will be censored at date $t_{1,I}$, where the low titre inhibitor is first detected.

For an analysis “time / number of EDs to inhibitor occurrence” for low titre inhibitors the time defined under (I4) is $t_{1,I}$. For this analysis patients with confirmed high titre inhibitor will be censored at minimum {date of $t_{1,H}$, date of $t_{1,I}$ } where the high titre inhibitor is first detected.

Peak inhibitor titre:

The peak inhibitor titre for each individual patient is defined as the maximum inhibitor titre measured by central lab at any timepoint during the study. This includes also the results of re-tests.

Inhibitor-free period:

An inhibitor is regarded as confirmed between start date as defined above (Definition “I4”) and the time when the inhibitor titre decreases back to <0.6 BU for the first time, which is to be confirmed by a subsequent measurement of <0.6 BU. If the inhibitor titre does not decrease to <0.6 BU during the study, the period with confirmed inhibitor will be counted until study end. Periods of time without confirmed inhibitor are regarded as “inhibitor-free”.

Prophylactic Treatment

Secondary objective: To assess the efficacy of Human-cl rhFVIII during prophylactic treatment.

Secondary endpoint: Monthly rate of spontaneous break-through bleeds during time of prophylactic treatment assessed as excellent, good, moderate or poor by the following scale:

Excellent: Less than 0.75 spontaneous BE per month.

Good: Between 0.75 and 1 spontaneous BE per month.

Moderate: Between more than 1 and 1.5 spontaneous BEs per month.

Poor: More than 1.5 spontaneous BEs per month.

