The time period for prophylactic treatment will comprise the time periods between first prophylactic treatment with *Human-cl rhFVIII* until the administration of the last prophylactic treatment + 14 days or completion visit (whichever comes first) minus time periods from start of a surgery until final assessment of the surgery, and minus time period of on-demand treatment, if any. All spontaneous BEs starting during the time periods for prophylactic treatment defined above will be included. BEs categorized as traumatic or as post-operative will not be included in the primary prophylactic treatment assessment.

Regarding BEs during or after surgery this is a general rule.

However, BEs emerging shortly after surgeries could be independent from the surgery, whereas a surgery-related BE could still emerge after the final assessment of the surgery. Therefore the final assessment of whether or not the BE is related to surgery (i.e. to be categorized as post-operative), and hence will be excluded from the BE incidence calculation for prophylactic treatment, will be made in the data review meeting before final database close.

In addition to the analyses described above, the analyses of bleeding rates will be performed in all patients during inhibitor-free periods.

Study drug consumption data (FVIII IU/kg BW, extrapolated to monthly and yearly usage) per subject will be evaluated.

3.4.2 **Bleeding Episodes (BEs)**

Secondary objective: To assess the efficacy of *Human-cl rhFVIII* during treatment of bleeds

Secondary endpoint: Efficacy assessment of bleeding episodes at end of a BE on a four point scale by the patient's parent(s)/legal guardian(s) (together with the Investigator in case of on-site treatment):

- Excellent:* Abrupt pain relief and/or unequivocal improvement in objective signs of bleeding within approximately 8 hours after a single infusion
- Good:* Definite pain relief and/or improvement in signs of bleeding within approximately 8 – 12 hours after an infusion requiring up to 2 infusions for complete resolution
- Moderate:* Probable or slight beneficial effect within approximately 12 hours after the first infusion requiring more than two infusions for complete resolution
- None:* No improvement within 12 hours, or worsening of symptoms, requiring more than 2 infusions for complete resolution

For all breakthrough BEs occurring during the study period, the following data will be documented or derived:

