- **Efficacy: Per Protocol (PP) analysis population**: All subjects in the ITT analysis population who completed the trial without significantly violating the inclusion/exclusion criteria or other aspects of the protocol considered to potentially affect the efficacy results.
Especially the following subjects will be excluded from this population:
 - Subjects who violate the following inclusion criteria:
 - severe haemophilia A (FVIII:C < 1%; historical value as documented in subject records),
 - no previous treatment with FVIII concentrate or other blood products containing FVIII
 - Subjects who fulfil at least one of the following exclusion criteria:
 - other coagulation disorder than haemophilia A
 - severe liver or kidney disease (ALT and AST levels >5 times of upper limit of normal, creatinine >120 $\mu\text{mol/L}$),
 - concomitant treatment with any systemic immunosuppressive drug,
 - Subjects who use concomitant medication that may confound study results, like e.g. alpha-interferon or prednisone
 - Subjects with significant non-compliances with the protocol like for example non-compliance to complete the diary in a proper manner or more than 30% of haemostatic efficacy assessments missing.

- Subjects with dosing or treatment errors like e.g. the use of other FVIII products (except for emergencies) or several *unexplained* and significant deviations from the recommended dose regimen.
- Subjects for whom less than a minimum of inhibitor tests is available*
- Patients with less than 95 days of exposure to *Human-cl rhFVIII*.

*Defined during Data Review Meeting for the interim analysis on April 7, 2016:

if less than 1 inhibitor test is available for any of the following periods:

- baseline, if first result of inhibitor screening after first exposure to the study drug is positive (it cannot be assured that the patient is a PUP),
- between ED2 and ED20,
- between ED21 and ED50.

- Population of subjects on prophylactic treatment schedule (PROPH): All subjects in the ITT population who have at least one prophylactic treatment. Only data under prophylaxis will be used for the analyses.
- Per-protocol population of subjects on prophylactic treatment schedules (PROPH-PP): All subjects in the PP population who have at least 95 EDs of treatment and who have no significant dosing or treatment errors, like e.g. unexplained interruptions of the prophylaxis with *Human-cl rhFVIII*.

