- Population of subjects on continuous prophylaxis (PROPHcont): All subjects in the ITT population who have at least one prophylactic treatment and have been assigned to the subgroup of patients receiving continuous prophylaxis, i.e. prophylactic treatment period of at least 169 calendar days, and have not received a mixture of on-demand and prophylactic treatment (however, subjects who were treated on-demand only once and switched to prophylactic treatment thereafter, will be kept in this population).
- Population of subjects with on-demand treatment (OD): All subjects in the ITT population with at least one period of on-demand treatment. Only data under on-demand treatment will be used for the analyses.
(Definition of period under OD: A patient in the main study is defined to be under prophylaxis during all time periods within 14 days after each prophylactic treatment. A patient in the main study is defined to be under OD in time periods he is not under “Prophylaxis” according to previous definition)
- Population of BEs (BLEED): All documented treated BEs of subjects in the ITT population for which
 - any amount of treatment with *Human-cl rhFVIII* is documented (either the treatment is indicated with reason “Bleeding” or ITI treatment and an efficacy assessment for the BE is documented).
 - start between first BE treated with *Human-cl rhFVIII* and the completion visit*Note*: Any type of BE is included: spontaneous, traumatic, post-operative or other

Additional to version 2.0 of the SAP, part of the analysis will be restricted to BEs during inhibitor-free periods.

- Population of BEs per protocol (BLEED-PP): All documented bleeds in the BLEED population of subjects in the PP population, which
 - are *not* treated with another FVIII or bypassing agents

Note: Any type of BE is included: spontaneous, traumatic, post-operative or other

Additional to version 2.0 of the SAP, part of the analysis will be restricted to BEs during inhibitor-free periods.

- Surgery population (SURG): All documented surgical interventions of subjects in the ITT population for which
 - any amount of *Human-cl rhFVIII* prior to, during or after the surgery is documented and
 - no other FVIII concentrate is documented within 24 hours prior to surgery*.
- Surgery per-protocol population (SURG-PP): All documented surgical interventions of subjects in the PP population for which
 - any amount of *Human-cl rhFVIII* prior to, during or after the surgery is documented and

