 - no other FVIII concentrate is documented within 72 hours prior to, during or after the surgery (until resuming regular prophylactic treatment or until discharge from hospital in case of a subject with on-demand treatment).

*For the analyses of surgeries only surgeries performed under *Human-cl rhFVIII* will be considered; clearly the assessment of the efficacy of *Human-cl rhFVIII* in surgeries should not be biased by inclusion of data from surgeries where other FVIII concentrates were used prior to the surgery.

Additional to version 2.0 of the SAP, part of the analysis will be restricted to surgeries during inhibitor-free periods.

- Infusions analysis population (Safety-INF): All documented infusions with *Human-cl rhFVIII* to subjects of the Safety population.
For the definition of temporally associated AEs: AEs will be related to a subject's infusion No. i, if the AE starts during infusion No. i or within 24 hours after infusion No. i, but before the same subject's infusion No. i+1.

The subject disposition, i.e. the identification of significant deviations to consider for the PP population and the assignment of each subject, bleeding and surgery to these analysis populations, will be the joined decision of the trial statistician and the responsible medical expert prior to database lock.

There may be further reasons to exclude patients from analysis populations without an underlying protocol deviation. This comprises:

- Patients withdrawn from study according to protocol with incomplete data.

The ITT analysis is considered to be most relevant for the analysis of immunogenicity data; the PROPH population is considered to be most relevant for the analysis of efficacy data on prophylaxis; the BLEED population is considered to be most relevant for the analysis of efficacy data on treatment of bleeds and the SURG population is considered to be the most relevant for the analysis of efficacy data on treatment during surgeries. To evaluate the robustness of the study results, efficacy analyses will also be done based on the PP population.

5.2 **Protocol Deviation Assessment**

Protocol deviations will be assessed as major or minor with respect to the analysis populations defined in section 5, and listed as part of the database release procedures prior to data analysis, and will include:

- Violation of inclusion or exclusion criteria
- Concomitant medication that may confound study results (see protocol chapter 4.2.2 Forbidden Concomitant Medication)

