16.2.6.1	L	Number of bleeding episodes, rate per month, rate per year, overall efficacy of prophylactic treatment, characteristics of BE (3 subtables for spontaneous, traumatic and all BEs + 3 subtables for prophylactic treatment in inhibitor-free period)	ITT
16.2.6.3	L	Bleeding episodes during study (including BEs in BLEED population and BEs not in BLEED population)	All BEs
16.2.6.4	L	Bleeding episodes, doses and changes in dose per infusion for each bleeding episode during study	BLEED, BLEED-PP
16.2.6.5	L	Bleeding episodes by site of BE, efficacy assessments, doses per BE and per infusion by site of BE	BLEED, BLEED-PP
16.2.6.6	L	Other per subject data on BEs in BLEED population	All
16.2.6.9.1.1	L	Surgeries: Description and outcome of surgical procedures	SURG, SURG-PP
16.2.6.9.1.2	L	Description and outcome of surgical procedures – Criteria for major severity, Hospitalization	
16.2.6.9.2	L	Surgeries: Description of wound hematoma yes/no and whether it needed surgical evacuation yes/no	SURG, SURG-PP
16.2.6.9.3	L	Surgeries: Description and assignment to SURG/SURG-PP populations including reasons for exclusion	SURG, SURG-PP
16.2.6.9.4	L	Surgeries: Blood loss (planned and actual), duration of surgery (planned and actual)	SURG, SURG-PP
16.2.6.10	L	Medical resource use data not covered in other listings: CVAD type, CVAD use, complications and management of the complications, hospitalization (including ward type) and duration	All
16.2.6.11	L	Additional health economic evaluation	All
16.2.7.1	L	Treatment-Emergent adverse Events (inc. indicator for phase of study: prophylactic, surgery, on-demand, ITI)	All
16.2.7.2	L	Possibly/probably related treatment-emergent adverse events (according to investigator and/or sponsor)	All
16.2.7.3	L	Non-treatment emergent adverse events	All
16.2.8.1	L	Laboratory assessments (Haematology, Clinical chemistry) (2 sub-listings: hematology, clinical chemistry)	All
16.2.8.2	L	FVIII:C, Inhibitors at baseline and during study	All
16.2.8.3	L	Confirmed occurrence of inhibitor, time from ED1 to confirmed inhibitor occurrence and number of EDs before inhibitor development, if any	All
16.2.8.4	L	Assessment of success in patients with inhibitors/ ITI therapy	ITI
16.2.8.5	L	Epitope mapping (in case of inhibitor development)	ITI
16.2.8.6	L	Vital signs	SAF
16.2.8.7.1	L	Physical examination	All
16.2.8.7.2	L	Abnormal findings of physical examination	SAF
16.2.9.1	L	Additional comments provided in the CRF	All

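### The excellent-to-poor prophylaxis rating has no minimum observation time, so in the lead set PROPH a patient observed for under about 20 days can only be rated Excellent or Poor

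*SAP*

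**What the plan says.** The secondary endpoint for prophylaxis (SAP 3.4.1, Prophylactic Treatment) is the monthly rate of spontaneous bleeds, graded on a four-point scale. It starts at "Excellent: Less than 0.75 spontaneous BE per month" and "Good: Between 0.75 and 1 spontaneous BE per month"; Moderate covers rates above 1 up to 1.5, and Poor covers anything above 1.5. Protocol 7.2.2.1 has the same cut-offs and says that the frequency "will be calculated and assessed as excellent, good, moderate or poor".

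Time on prophylaxis runs from the first prophylactic dose "until the administration of the last prophylactic treatment + 14 days or completion visit", less surgery periods and on-demand time. No minimum is stated there or in SAP 9.2.

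PROPH is defined in SAP 5.1 as "All subjects in the ITT population who have at least one prophylactic treatment. Only data under prophylaxis will be used for the analyses". The same section says that "the PROPH population is considered to be most relevant for the analysis of efficacy data on prophylaxis". A duration limit exists only for the supportive set PROPHcont, which needs a "prophylactic treatment period of at least 169 calendar days". PROPH-PP needs at least 95 exposure days of treatment.

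Listing 16.2.6.1 (SAP 13) sets out "Number of bleeding episodes, rate per month, rate per year, overall efficacy of prophylactic treatment" together, with further subtables for inhibitor-free periods. This points to a rating for each patient.

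**The concern.** A rate taken over a very short period can take only a few values. With no minimum time, the four-point scale is applied to patients for whom two of its categories are impossible, and the result depends on whether one bleed happened to fall in a couple of weeks.

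Short periods can be foreseen. Protocol 5.4 lets patients move between prophylaxis and on-demand treatment, and on-demand time is subtracted. Protocol 1.1 expects inhibitors in up to about 30% of these patients, usually within the first 50 exposure days, and an inhibitor can lead to immune tolerance induction or withdrawal. The prophylaxis tables are also repeated for inhibitor-free periods, which can shorten the window further.

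At stake is the meaning of the graded endpoint in the lead set: ratings based on two weeks and on half a year would be read as the same kind of evidence.

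**Working it through.** The plan states no operating characteristics for the scale, so there is no figure of its own to reproduce.

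**Inputs.** Cut-offs 0.75, 1 and 1.5 per month (SAP 3.4.1). A one-dose patient has T = 14 days (SAP 3.4.1; SAP 5.1 also counts a patient as under prophylaxis for 14 days after each prophylactic dose). PROPHcont minimum: 169 days (SAP 5.1). One month = 365.25/12 = 30.44 days. Assumed: bleeds are Poisson with a constant true rate λ. The documents give no untreated spontaneous bleed rate, so λ is shown over a range.

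**Step 1: reachable categories (no bleeding rate needed).** The rating depends on k/T, with k bleeds in T months. k = 0 is always Excellent. k = 1 is Poor whenever 1/T > 1.5, that is T < 2/3 month = 20.3 days. Below that, Good and Moderate cannot occur. At 14 days T = 14/30.44 = 0.460, and one bleed gives 1/0.460 = 2.17 per month. One bleed alone is then Moderate from 20.3 to 30.4 days, Good from 30.4 to 40.6 days, and Excellent beyond that.

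**Step 2: chance of each category.** At 14 days, P(Excellent) = exp(−0.460λ) and P(Poor) is the remainder. At 169 days T = 5.55; Excellent needs k ≤ 4 (4/5.55 = 0.72, 5/5.55 = 0.90) and Poor needs k ≥ 9 (8/5.55 = 1.44, 9/5.55 = 1.62).

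| λ per month (assumed) | Excellent, 14 d | Poor, 14 d | Excellent, 169 d | Poor, 169 d |
|---|---|---|---|---|
| 0.5 | 79% | 21% | 85% | 0.2% |
| 1.0 | 63% | 37% | 35% | 11% |
| 1.5 | 50% | 50% | 8% | 45% |
| 2.0 | 40% | 60% | 1% | 78% |

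**Step 3: what an Excellent from zero bleeds says.** The two-sided 95% upper limit for the rate is −ln(0.025)/T = 3.69/0.460 = 8.0 bleeds per month at 14 days, more than five times the Poor boundary.

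**Step 4: when Excellent is the likelier result in a short window.** exp(−λT) > 0.5 requires λ < 0.693/T. That is 1.51 per month at 14 days and 1.05 at 20 days (T = 0.657). At 20 days and λ = 1.5, P(Excellent) = exp(−0.986) = 37%.

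**Step 5: shortest time at which the scale always works.** Good needs a whole number of bleeds between 0.75T and T. For T between 2.67 and 3 months that interval lies strictly between 2 and 3, so Good is impossible. From T = 3 months (91.3 days) upward, all four categories are always reachable.

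**The case against.** The strongest reply is that the plan does not rest on the grade. SAP 9.2 asks for the number and rate of bleeds and does not mention the categories. The efficacy tables in SAP 13 (14.2.19.1.1.1 onward) are titled by rate with a 95% confidence interval, and Poisson annualized rates are planned in PROPH (14.2.19.7.1). The same efficacy table is run in PROPHcont and PROPH-PP. Nowhere do the documents announce a share rated Excellent as the main result. With a 14-day tail, fewer than 20.3 days overall also means first and last prophylactic doses no more than about 6 days apart, unless completion, surgery or on-demand time cuts the window. Few patients may fit that.

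Most of this stands, and it limits the weight of the point. It does not remove it. SAP 3.4.1 still makes the graded rate the endpoint, and PROPH is still the lead set. The 169 days in PROPHcont refers to the whole prophylactic period, not to the inhibitor-free part of it. The 95 exposure days in PROPH-PP are, as worded, days of treatment and not a minimum time on prophylaxis. For time with a confirmed inhibitor, the table titles name only rates, so grading in that window is an inference.

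**Conclusion.** The defect holds as a matter of arithmetic: the rating has no minimum time, the lead set admits one-dose patients, and below about 20 days only Excellent and Poor exist. The probabilities rest on Poisson bleeds and on the assumed range of 0.5 to 2.0 per month. The effect on the overall result cannot be derived, because the number of short-period patients is unknown. This is worth changing because the change is cheap; it is not shown to distort the trial's conclusion.

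A reader might go further and infer that short-period patients come out mostly Excellent even if prophylaxis has no effect, so that the scale flatters the product. The documents do not support this. They give no untreated rate, and Excellent is the likelier result only below 1.51 per month at 14 days and 1.05 at 20 days. Nor is the error one-sided: at a true 0.5 per month the short window lowers the chance of Excellent (79% against 85%) and raises that of Poor (21% against 0.2%).

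**What to change.** 1. In SAP 3.4.1 and 9.2, assign a category only if prophylaxis time in the window being analysed (overall or inhibitor-free, and time with an inhibitor if that is graded) reaches a stated minimum. The 169 days already used for PROPHcont is a natural choice; about 3 months is the least at which all four categories are always reachable.
2. Show the remaining patients as 'not rated (short observation)', and print observation time beside every rating.
3. Keep the bleeds and time of all PROPH patients in the planned Poisson rate. Define it for spontaneous bleeds as total bleeds over total prophylaxis time, and present it with its 95% confidence interval as the lead result. The titles of the Poisson tables mention neither bleed type nor interval, so the SAP should state both.
4. Separately, reconcile two differences between the documents. The SAP window ends 14 days after the last prophylactic dose and the protocol's (7.2.2.1) ends 2 days after, so a bleed between those points counts under one and not under the other. The protocol also ties the rating to three-times-weekly or every-other-day prophylaxis, a limit that the SAP definition omits.

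The cost is SAP wording and a time filter on existing tables; no new data are needed. The downside is selection: the rated patients are those who stayed on prophylaxis, and those who stopped early, for instance because of an inhibitor, drop out of the grading. The number not rated and the reasons should therefore be shown. An on-demand bleeding rate should not be added as a yardstick, because Protocol 5.4 leaves the regimen to the physician and allows switching.
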